Cross-cultural validation of the FS-ICU has been conducted in North America⁸ and Switzerland¹⁴ but not in the UK. The measurement properties of the instrument needs to be fully understood, including interpretation of the scores, what constitutes clinically or socially meaningful differences in scores, as an important and necessary pre-requisite before its introduction into quality improvement programmes in the NHS. In the UK, the feasibility and acceptability of using the FS-ICU has been assessed in a single centre pilot study and, of 146 questionnaires distributed, 95 were returned (response rate 66%) and with 71 (75%) rating the acceptability of the questionnaire as "very good" to "excellent".¹⁵ In addition, if meaningful comparisons of providers are going to be made then other issues need to be addressed: representativeness of the family members included; the sampling frame and sample size required; and the relationship between family experience and patient outcome.

There is no doubt that the benefits of gaining information and insights from family members could revolutionise quality improvement in adult critical care. However, current enthusiasm for involving patients and family members in measuring the humanity and effectiveness of adult critical care should not obscure the challenges. The Family Reported Experiences Evaluation (FREE) Study hopes to address these challenges for adult critical care services in the NHS by measuring family members' views in a systematic and rigorous manner as a first step to incorporating them into clinical practice.

The Department of Health has indicated that patients' views are essential to achieving high quality care.¹³ The FREE Study directly addresses the challenges of incorporating patients' views in critical care by incorporating family members' views (in recognition of the fact that a representative sample of patients' views is unachievable), into quality improvement of adult critical care services. There is considerable evidence that the need to continue to involve patients/family members will be sustained within policy for the future. The FREE Study is a necessary precursor to directly incorporating routine surveying of family members' views into a quality improvement programme for adult critical care services in the UK. Routine feedback should lead to improved organisation and delivery of critical care services in the NHS.

3. Study aim and objectives

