The overall aim of the FREE Study is to inform valid, representative and cost-effective future use of the FS-ICU questionnaire into quality improvement programmes for adult critical care services in the NHS in the UK.

The objectives of the FREE Study are:

- to test the face and content validity and the comprehensibility of the FS-ICU;
- to establish the internal consistency, construct validity and reliability of the FS-ICU;
- to describe family satisfaction using the FS-ICU and explore how family satisfaction, measured with the FS-ICU, varies by:
 - family member;
 - patient characteristics;
 - unit/hospital characteristics;
 - other contextual factors; and
 - country (through comparison with FS-ICU data held in Canada);
- to model approaches to sampling to achieve representative sampling for feasible, cost effective future use of the FS-ICU in quality improvement in the NHS.

4. Study design

The FREE Study is a mixed methods study comprising a psychometric evaluation (FREE-Qual) leading to a multicentre cohort study.

The objectives of the FREE Study will be addressed in two sub-studies.

FREE-Qual

FREE-Qual is a qualitative study (see: Section 5) which will address the first objective by testing the face and content validity and the comprehensibility of the validated Canadian FS-ICU. Modifications to the FS-ICU questionnaire will then be made, if required.

The FREE Study

FREE is a multicentre cohort study (see: Section 6) which will address the remaining objectives using the UK adaptation of the FS-ICU questionnaire (FREE-Qual).

Staff at twenty adult, general critical care units will identify up to four family members for consecutive patients admitted to their unit who stay more than 24 hours. Family members who consent to take part will be sent a questionnaire three weeks following patient discharge from the critical care unit.

The recruitment period will be one year, chosen to avoid bias from seasonal variation in case mix and workload. A psychometric assessment of the FS-ICU will be undertaken using data collected during the first month.

5. FREE-Qual

Research Ethics Committee reference:	12/YH/0415
Sponsor reference:	ICNARC/02/05/12
NIHR CRN Portfolio ID number:	112459
Protocol version:	1.0
Protocol version date:	31 July 2012

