Internal consistency will be evaluated through calculation of item-total correlations and Cronbach's alpha.¹⁶ Item-total correlations <0.4 or Cronbach's alpha <0.8 will be taken as indicative of potential lack of internal consistency.

Validity analysis

The criterion validity of the FS-ICU among family members of non-survivors will be assessed by comparison with the QODD questionnaire.¹⁷ All family members of non-survivors during the first month will be sent a QODD questionnaire along with the FS-ICU. The hypotheses that will be tested are that higher values for the two summary domain scores of the FS-ICU (satisfaction with care and satisfaction with decision-making) are associated with higher values for the overall QODD score, and that scores on four specific items in the QODD (pain control, breathing comfort, care by doctors, care by all providers⁸) will be moderately correlated with FS-ICU scores. No sufficiently well-validated measure exists to conduct a validity analysis of the FS-ICU among family members of critical care survivors.

Main analysis

Family satisfaction will be described by summarising the responses to the 24 individual questionnaire items of the FS-ICU and the two summary domain scores for satisfaction with care and satisfaction with decision-making. Variation in satisfaction across the critical care units will be summarised by presenting the domain scores for each unit, anonymised, in the form of funnel plots,¹⁸ both before and after adjustment for family member, patient and unit/hospital characteristics.

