Variation in family satisfaction by: family member characteristics (e.g. relationship to the patient); patient/admission characteristics; unit/hospital characteristics; and other contextual factors will be explored using multilevel linear regression modelling. The outcomes for the regression models will be the two domain scores for satisfaction with care and satisfaction with decision-making. Models will be stratified by the survival status of the patient at discharge from the critical care unit. The levels of the model will be: level 1, family member; level 2, patient/critical care unit admission; level 3, unit/hospital. Family member characteristics entered into the models will include: age; sex; and relationship to the patient. Patient/admission characteristics will include: age; sex; severe chronic conditions in the past medical history; surgical status (elective surgery, emergency surgery, non-surgical); acute severity of illness (ICNARC Physiology Score¹⁹); and length of stay in the critical

care unit. Unit/hospital characteristics will include: teaching status; and number of beds in the critical care unit. Contextual factors will include: month of the year (seasonality). Non-linearity in the relationship between continuous predictors and satisfaction will be modelled using restricted cubic splines.

Variation in family satisfaction by country will be explored by comparing data collected for the FREE study with FS-ICU data from Canada (and available to [name]) in the context of a multilevel linear regression model with a similar structure to that above. Country comparisons will be adjusted for the age, sex and relationship to the patient of the family member and for patient characteristics consistently recorded in the different datasets.

As routinely surveying family members of all patients admitted to a critical care unit would neither be feasible nor cost-effective, understanding the association between patient factors and family satisfaction will enable an appropriately stratified sampling frame to be explored and developed.

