13.2 Study results

The results of the FREE Study will be widely and actively disseminated.

Staff from participating units will be invited to a Collaborators' Meeting at which the results of the FREE Study will be presented. All participating units will receive individual, comparative reports on family satisfaction. Variation in family satisfaction across critical care units will be summarised by presenting the domain scores for each unit, anonymised, in the form of funnel plots, both before

and after adjustment for family member, patient and unit/hospital characteristics. Feedback will be elicited from critical care unit staff attending the Collaborators' Meeting on the best mode of presentation with a view to maximizing the potential for using the results to improve quality.

ICNARC has access to both patients and their families and close friends from its recent support and collaboration in three modules (http://www.healthtalkonline.org/Intensive_care/) for the award winning website healthtalkonline (<http://www.healthtalkonline.org/>) and through its work with ICUsteps, the intensive care patient support charity, on the FREE Study. ICNARC has established strong links with the critical care community, which includes: a large network of NHS critical care units (>200) in the UK through its National Audit Programme and CTU; close links with the Intensive Care Society (ICS), the representative body in the UK for critical care professionals (ICNARC has representation on the ICS Council and membership of the ICS Research Committee); close links with the British Association of Critical Care Nurses (BACCN) and the Royal College of Nursing Critical Care and In-flight Nursing Forum (RCN CCINF); representation on the NIHR Comprehensive Clinical Research Network Critical Care Specialty Group.

The final report to the NIHR HS&DR Programme will present a detailed description of the FREE Study and the results along with recommendations for future policy and practice and future research. The results of the FREE Study will be presented at: regional critical care network meetings; national professional conferences (e.g. ICS, BACCN, RCN CCINF); the Annual Meeting of the ICNARC Case Mix Programme; the Annual Meeting of the UK Critical Care Research Forum; and at national and international critical care conferences/meetings.

References

1. Department of Health. *Equity and excellence: Liberating the NHS*. London: The Stationery Office Limited, 2010.

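### The only adjusted funnel plot also adjusts for unit/hospital characteristics, so it removes part of the between-unit variation it is meant to summarise, and no case-mix-only plot is described

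*Protocol*

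**What the plan says.** Protocol section 7.2 (Main analysis) gives the purpose of the plots: "Variation in satisfaction across the critical care units will be summarised by presenting the domain scores for each unit". It describes two versions, "both before and after adjustment for family member, patient and unit/hospital characteristics". Section 13.2 (Study results) repeats the pair, "and after adjustment for family member, patient and unit/hospital characteristics", directly after promising each participating unit a comparative report.

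The regression paragraph of 7.2 lists the covariates: "Unit/hospital characteristics will include: teaching status; and number of beds in the critical care unit". It adds that "Non-linearity in the relationship between continuous predictors and satisfaction will be modelled using restricted cubic splines". The model keeps a unit level ("level 3, unit/hospital"), and the same models are used to explore how satisfaction varies with unit and hospital characteristics.

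Section 4 fixes the number of units: "Staff at twenty adult, general critical care units will identify up to four family members". The Background gives provider comparison as a motive: "if meaningful comparisons of providers are going to be made then other issues need to be addressed".

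No plot adjusted for family member and patient characteristics alone is described.

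**The concern.** A funnel plot that compares providers needs adjustment for who was treated and who answered, so that what remains can be read as a difference between units. Teaching status and bed number belong to the unit itself. Once they are in the adjustment set, each unit is judged against units of its own type and size. A difference that families experienced because of unit type or size disappears from the adjusted plot.

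Because the two kinds of adjustment come as a package, the before/after pair cannot separate them. If a unit moves between the plots, the reader cannot tell whether case mix, respondent mix or provider type moved it. The quantity most useful to a unit receiving feedback, its score after allowing for its patients and respondents, is shown in neither plot.

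The country comparison in 7.2 provides a contrast within the protocol. It names family member and patient characteristics for adjustment and no unit characteristics.

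**Working it through.** The plan gives no figure for this point, so there is none to reproduce. The inputs come from protocol sections 4, 7.1 and 7.2; assumptions are marked.

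**1. Variation absorbed by chance**

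- 20 units give 20 − 1 = 19 between-unit degrees of freedom.
- Teaching status uses 1. Beds use 1 if linear, or 2, 3 or 4 with a restricted cubic spline of 3, 4 or 5 knots. The number of knots is not stated, so this range is an assumption.
- If neither factor has any true effect, the expected share absorbed is terms/19: 2/19 = 10.5%, 3/19 = 15.8%, 4/19 = 21.1%, 5/19 = 26.3%.
- Simulation agrees. Twenty unit effects were regressed on teaching status and beds, with 3,000 replicates per setting, giving mean shares of 10.4%, 15.9%, 21.6% and 26.2%.

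**2. Variation absorbed when the factors matter**

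The same simulation assumed 8 of 20 teaching units and a bed distribution that is not in the documents:

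| True share explained by type and beds | Mean share removed (linear beds to 5 knots) |
|---|---|
| 0 | 10-26% |
| 0.2 | 28-41% |
| 0.5 | 56-63% |
| 0.8 | 83-86% |

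The mean share removed stays below 100% in every setting.

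**3. Precision of a unit mean**

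- Section 7.1 (revised) gives about 8,500 responses from 5,500 patients, with SD 20. That is 8,500/20 = 425 responses per unit and 8,500/5,500 = 1.55 responses per patient.
- SE = 20 × √(DEFF/425), where DEFF = 1 + 0.545 × ICC. The within-patient ICC is not given, so its full range is shown.
- ICC 0: SE = 0.97. ICC 0.5: DEFF 1.27, SE = 1.09. ICC 1: DEFF 1.55, SE = 1.21.
- The 95% limits are therefore about ±1.9 to ±2.4 points.

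**4. How far adjustment moves a unit**

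The documents give no teaching/non-teaching difference. Assume a gap *g* and an even split. Adjustment then re-centres each type on the overall mean, so each unit moves *g*/2. Take a unit 3 SE below average:

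| Gap *g* | Shift | Shift in SE | Plotted position if in the worse-rated type | If in the better-rated type |
|---|---|---|---|---|
| 1 point | 0.5 | 0.41-0.52 | 2.48-2.59 SE low | 3.41-3.52 SE low |
| 2 points | 1.0 | 0.83-1.03 | 1.97-2.17 SE low | 3.83-4.03 SE low |
| 4 points | 2.0 | 1.66-2.06 | 0.94-1.34 SE low | 4.66-5.06 SE low |

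Such a unit falls inside the 95% limits only if *g*/2 exceeds (3 − 1.96) × SE. That means *g* above 2 × 1.04 × 0.97 = 2.0 points to 2 × 1.04 × 1.21 = 2.5 points.

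**5. If the plots follow the survival strata**

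Section 7.2 stratifies the models by survival status. If the plots do the same, and one third of responses concern non-survivors (an assumption), a unit has 425/3 ≈ 142 such responses. The SE is then 20/√142 = 1.68 at ICC 0, and 1.68 × √1.55 = 2.09 at ICC 1. A 2-point shift would be about 1.0-1.2 SE.

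**The case against.** A reader might infer that the adjusted plot wipes out the between-unit differences, or that poorly rated units will be hidden. The documents do not support either. Only the part explained by the unit covariates is removed. Unit remains as the third level of the model, and the unadjusted plot is shown alongside. The shift works in both directions: a low-scoring unit in the better-rated type becomes more conspicuous.

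The plan can also be defended on purpose. One objective is to explore how satisfaction varies by unit and hospital characteristics, and a before/after pair shows how much variation the measured factors explain. Units are anonymised, no outlier rule or sanction is attached to the plots, and section 13.2 invites staff feedback on presentation. That the comparative reports contain the adjusted plot is an inference from adjacent sentences. Section 6.2 selects units by stratified random sampling and gives teaching status as an example of the representativeness sought. Teaching status and size may also stand in for case mix that the patient covariates miss.

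These arguments justify keeping a fully adjusted plot. They do not justify making it the only adjusted one. The multilevel models already estimate the associations with teaching status and bed number, so the exploratory aim does not depend on this plot. None of the arguments supplies a plot that shows units after allowance for patients and respondents alone.

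**Conclusion.** The point holds as a partial masking of unit differences and a missing display. The plan fixes two funnel plots, and neither isolates case-mix-adjusted differences between units, although provider comparison is a stated motive.

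By chance alone the adjusted plot absorbs about 10-26% of between-unit variation; this range rests on linear beds or 3 to 5 knots. Any real association with unit type or size adds to it, by an amount the documents do not allow one to fix. A 4-point gap would bring a unit 3 SE low in the worse-rated type well inside the 95% limits. A gap of 1 point would not, and the crossover is about 2.0-2.5 points with 425 responses per unit. Section 7.1 uses 4 points for a binary patient factor, so it is not evidence of a gap between unit types.

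A reader might also want length of stay removed from the adjustment as something the unit influences. Section 7.2 lists it as a patient/admission characteristic, and nothing in the protocol supports treating it otherwise.

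**What to change.** In sections 7.2 and 13.2, define the main adjusted funnel plot as adjusted for family member and patient characteristics only. Keep the version that adds teaching status and number of beds as an extra plot, labelled as explanatory: it shows what remains once unit type and size are also accounted for.

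The regression analysis of unit characteristics stays as it is. The change needs no new data. It costs a wording change in two sections and one additional model fit and plot per domain score (per survival stratum, if the plots are stratified).

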7.1 Sample size and recruitment rate calculation

The duration of recruitment will be one year, chosen to avoid bias from seasonal variation in case mix and workload. Data from the CMP database indicates that an average of 520 patients are admitted per unit, per year, and of these, 74% stay at least 24 hours, corresponding to 7,700 patients (approximately 19,250 family members). Assuming an average of 2.5 family members per patient and a 66% response rate,¹⁵ a total sample of approximately 12,700 responses, associated with 6,700 patients will be achieved. Using available FS-ICU data, published and unpublished, we anticipate mean baseline satisfaction domain scores of 80 with standard deviation 20. This sample size will give >90% power to detect ($p<0.01$) a binary patient factor present in 10% of the patient population associated with an increase or decrease in domain score of 4 points.

The sample size estimate was updated following completion of the first full quarter of recruitment, based on the CMP data submitted for that quarter from the actual participating sites and FREE Study data collected. Revised targets were calculated for each site based on successful recruitment of an average of 2 family members for 80% of patients staying at least 36 hours¹ in the critical care unit, allowing that on average 10% of patients may have no family members visit. Based on these revised targets, we anticipate recruitment of 14,200 family members (of 7,100 patients). Assuming a 60% response rate, a total sample of approximately 8,500 responses associated with 5,500 patients will be achieved. This sample size retains >90% power to detect ($p<0.01$) a binary patient factor present in 10% of the patient population associated with an increase or decrease in domain score of 4 points.

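### The spline rule for continuous predictors does not exempt number of beds, a unit-level variable with at most 20 values, so the adjusted unit comparison is mildly over-fitted

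*Protocol*

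**What the plan says.** The main analysis in Protocol section 7.2 is a three-level linear model, with levels given as "level 1, family member; level 2, patient/critical care unit admission; level 3, unit/hospital". Its unit-level predictors are named: "Unit/hospital characteristics will include: teaching status; and number of beds in the critical care unit". The same paragraph ends with the rule on functional form: "Non-linearity in the relationship between continuous predictors and satisfaction will be modelled using restricted cubic splines". It makes no distinction by level and gives no number of knots.

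The number of units is fixed in section 4: "Staff at twenty adult, general critical care units will identify up to four family members". Section 7.2 adds that "Models will be stratified by the survival status of the patient at discharge from the critical care unit". There are two domain scores as outcomes, so four models result, each with at most 20 units.

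The unit characteristics also enter the comparison of units. Funnel plots of domain scores are to be shown "both before and after adjustment for family member, patient and unit/hospital characteristics", and section 13.2 repeats this alongside individual comparative reports to participating units. The analysis is presented as exploratory: variation by unit characteristics and "other contextual factors will be explored using multilevel linear regression modelling".

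**The concern.** Splines are well supported for family-member age, patient age, physiology score and length of stay, each recorded on thousands of people. Number of beds is different. It is constant within a unit, so it has at most 20 values however many questionnaires come back. A restricted cubic spline with 3 to 5 knots spends 2 to 4 degrees of freedom on it, and teaching status takes one more, out of 19 between units.

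Two things are at stake. First, a flexible curve through so few points follows chance differences between units, so adjusted unit results look more alike than they should. Second, any test of the bed-number effect rests on very few residual degrees of freedom, and a large-sample reference distribution then rejects too often. How satisfaction varies with unit and hospital characteristics is one of the study's stated objectives (section 3).

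**Working it through.** **The plan's own figure.** Section 7.1 claims more than 90% power at p<0.01 (taken as two-sided) for a binary patient factor with 10% prevalence and a 4-point effect, assuming "mean baseline satisfaction domain scores of 80 with standard deviation 20".
- On 5,500 patients: SE = 20 × √(1/550 + 1/4,950) = 0.899, and 4/0.899 − 2.576 = 1.87, so power is 97.0%.
- On 8,500 responses treated as independent: SE = 0.723, and power is 99.8%.

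The claim reproduces, but it concerns a patient-level factor and says nothing about terms that vary only between units.

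**Inputs for the unit-level check.**
- From the protocol: 20 units, an intercept, teaching status (1 df) and number of beds (q df).
- Assumed: 3, 4 or 5 knots, giving q = 2, 3 or 4. A linear term has q = 1.
- Residual between-unit df = 20 − 1 − 1 − q = 18 − q. The analytic results treat units as balanced.

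**Over-fitting.** With no true unit-level effect, the expected share of between-unit variance absorbed by teaching status plus beds is (q + 1)/19. The remaining spread relative to the linear model is √[(18 − q)/17] in SD.

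| Bed term | q | Absorbed by chance | SD relative to linear |
|---|---|---|---|
| Linear | 1 | 2/19 = 10.5% | 1 |
| 3 knots | 2 | 3/19 = 15.8% | √(16/17) = 0.970 (3% narrower) |
| 4 knots | 3 | 4/19 = 21.1% | √(15/17) = 0.939 (6% narrower) |
| 5 knots | 4 | 5/19 = 26.3% | √(14/17) = 0.907 (9% narrower) |

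**Size of the bed-number test, if a large-sample reference is used.** Let c be the chi-square critical value on q df.
- REML Wald: size = P[F(q, 18 − q) > c/q].
- ML likelihood ratio: size = P[F(q, 18 − q) > (exp(c/20) − 1)(18 − q)/q].

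| Bed term | c at 5% | REML Wald | ML likelihood ratio |
|---|---|---|---|
| Linear | 3.841 | 6.7% | 7.5% |
| 3 knots | 5.991 | 7.9% | 9.1% |
| 4 knots | 7.815 | 9.0% | 10.9% |
| 5 knots | 9.488 | 10.2% | 13.2% |

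At nominal 1%, either test runs at about 2% for a linear term and about 4% with 5 knots.

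**Simulation check.** About 1,500 data sets per setting were simulated with unequal unit sizes. The assumptions, none of them in the protocol, were a unit ICC of 0.01, 0.03 or 0.10, skewed bed numbers with median about 13, and 8 teaching units.
- Across linear and spline terms, size was 6% to 10% for Wald and 7% to 13% for likelihood ratio, in line with the table.
- With an F reference on 18 − q df, size was 4% to 6% for the linear term and for every spline.
- Average leverage of the largest unit rose from about 0.41 (linear) to 0.61, 0.72 and 0.76 with 3, 4 and 5 knots. Its adjusted position is then largely its own fit.

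**The case against.** A reader might infer that the protocol commits itself to an anti-conservative test of bed number. It does not. It names no test, estimator, reference distribution or df method for this term, and the p<0.01 in section 7.1 belongs to a patient factor. Those choices, like the number of knots, can properly sit in a statistical analysis plan. An F reference with unit-level df holds the size near 5% even with a spline. Higher rates can be produced, for example 16% to 21% by pairing ML variance estimates with a Wald chi-square and 4 to 5 knots, but only by stacking choices the protocol does not make.

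A reader might also blame the spline for all of the inflation. A linear term already runs at 6.7% to 7.5% under the same large-sample tests, so the small number of units is the root cause.

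Nor do the documents support the reading that real unit differences will be hidden. The funnel plots are shown before adjustment as well as after, and the extra narrowing against a linear term is only 3% to 9%. Part of the 16% to 26% is due to teaching status, which is in the model either way.

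Finally, the sentence can be read as naming the method to use where non-linearity is present. That softens the point without removing it, because screening 20 units for curvature still lets chance choose the shape. What also stands is the scope of the rule: as written it covers bed number, and an F reference corrects the p-value but not the over-fitted curve.

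**Conclusion.** The point holds in a limited form and is minor. Taken literally, the stated rule puts a 2 to 4 df curve on a variable with at most 20 values and feeds it into the adjusted unit comparison. The cost is an expected 16% to 26% of between-unit variance absorbed by chance, against 10.5% with a linear bed term. These figures assume 3 to 5 knots, balanced units and no true unit-level effect. The inflated false-positive rate (7.9% to 10.2% for REML Wald, 9.1% to 13.2% for ML likelihood ratio, at nominal 5%) is conditional on a large-sample test being used. The splines for family- and patient-level predictors, the unadjusted funnel plots and the power statement are not affected.

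**What to change.** In section 7.2, limit the spline rule to continuous predictors measured on family members and patients. Enter number of beds as a single linear (or log) term. State that unit-level terms are tested against a t or F reference with small-sample degrees of freedom, for example Kenward-Roger; with teaching status and a linear bed term that is about 20 − 3 = 17. Both parts are needed: the single term limits the over-fitting, and the df method corrects the test, which a linear term alone would leave at 6.7% to 7.5%.

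The cost is one sentence and a software option, with no change to data collection or sample size. The downside is that a curved relation between bed number and satisfaction could not be described, though 20 units give little basis for describing one.
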